4. ELIGIBILITY

4.1 Inclusion Criteria

For inclusion in the study, patients must fulfil the following criteria:

1. Relapsed or refractory Diffuse Large B-Cell Lymphoma (DLBCL) relapsing after at least 1 course of potentially curative, anti-CD20 antibody containing regimen (e.g. RCHOP, GCHOP, RGCVP). High grade transformation from low grade lymphoma (e.g. follicular lymphoma, lymphoplasmacytic lymphoma, chronic lymphocytic leukaemia) is permitted but patients must have been treated for the high grade disease with at least one course of treatment as detailed above. Patients must have relapsed post-ASCT or be considered not suitable for ASCT.

2. Tissue biopsy (or bone marrow trephine if no other tissue available) confirming histology within 3 months of enrolment.

3. Provision of signed and dated, written informed consent prior to any study specific procedures, sampling and analyses.

4. Aged at least 18 years.

5. Eastern Cooperative Oncology Group (ECOG) performance status of \leq 2.

6. Females should be using adequate contraceptive measures (as described protocol section 5.3, different for patient receiving rituximab*), should not be breast feeding and must have a negative pregnancy test prior to start of dosing if of child-bearing potential or must have evidence of non-child-bearing potential by fulfilling one of the following criteria at screening:

- Post-menopausal defined as amenorrhoeic for at least 12 months following cessation of all exogenous hormonal treatments

- Documentation of irreversible surgical sterilisation by hysterectomy, bilateral oophorectomy or bilateral salpingectomy but not tubal ligation

* See section 5.3 of the protocol

7. Male patients should be surgically sterile or willing to use barrier contraception (i.e. condoms) as described in the protocol, (different for patient receiving rituximab*)

8. Ability to swallow and retain oral medication

9. CT measurable disease with at least 1 lesion having longaxis \geq 1.5cm or splenomegaly \geq 14cm in cranio-caudal length attributable to relapsed lymphoma

10. Patients must have negative virology for HIV.

11. For patients receiving single agent AZD2014 treatment only :

- Hepatitis C serology must be negative

- Hepatitis B serology must not indicate active infection. Specifically:

Patients who are hepatitis B surface antigen positive are excluded

Patients who are anti-hepatitis B sAg antibody positive in the absence of anti-core antibody are eligible if hepatitis B DNA is negative.

Patients who are positive for anti-hepatitis B core antibody (with no surface antigen) are eligible if hepatitis B DNA is negative.

- 12. For the rituximab cohort only:
 - Hepatitis C serology must be negative
 - Hepatitis B surface antigen and anti-core antibody must be negative

- Patients with a history of vaccination to hepatitis B and who are positive for anti-hepatitis B sAg antibody but negative for anti-core antibody are eligible if hepatitis B DNA is negative

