7. Male patients should be surgically sterile or willing to use barrier contraception (i.e. condoms) as described in the protocol, (different for patient receiving rituximab*)

8. Ability to swallow and retain oral medication

9. CT measurable disease with at least 1 lesion having long axis \geq 1.5cm or splenomegaly \geq 14cm in cranio-caudal length attributable to relapsed lymphoma

10. Patients must have negative virology for HIV.,

11. For patients receiving single agent AZD2014 treatment only :

- Hepatitis C serology must be negative
- Hepatitis B serology must not indicate active infection. Specifically:
- Patients who are hepatitis B surface antigen positive are excluded

Patients who are anti-hepatitis B sAg antibody positive in the absence of anti-core antibody are eligible if hepatitis B DNA is negative.

Patients who are positive for anti-hepatitis B core antibody (with no surface antigen) are eligible if hepatitis B DNA is negative.

12. For the rituximab cohort only:- Hepatitis C serology must be negative

- Hepatitis B surface antigen and anti-core antibody must be negative

- Patient with a history of vaccination to hepatitis B and who are positive for anti-hepatitis B sAg antibody but negative for anti-core antibody are eligible if hepatitis B DNA is negative

Exclusion Criteria

Patients must not enter the study if any of the following exclusion criteria are fulfilled:

 Prior chemotherapy, biological therapy, radiation therapy, androgens, thalidomide, immunotherapy, other anticancer agents, and any investigational agents within 21 days of registration (not including palliative radiotherapy at focal sites to non-target lesions). Corticosteroids are permitted during screening but should be weaned down to a maximum dose of prednisolone 10mg daily (or equivalent) by day 1 of cycle 1.

- With the exception of alopecia, any unresolved toxicities from prior chemotherapy should be no greater than CTCAE (Version 4.0) Grade 2 at the time of registration.

- 2. Major surgery within 4 weeks prior to entry to the study (excluding placement of vascular access), or minor surgery within 2 weeks of entry into the study.
- 3. Exposure to potent or moderate inhibitors or inducers of CYP3A4/5, Pgp (MDR1) and BCRP if taken within the stated washout periods before the first dose of study treatment. See Appendix 2.

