APPENDIX 1 – REVISED RESPONSE CRITERIA FOR MALIGNANT LYMPHOMA

Revised Criteria for Response Assessment

Response and Site	PET-CT–Based Response	CT-Based Response
Complete	Complete metabolic response	Complete radiologic response (all of the following)
Lymph nodes and	Score 1, 2, or 3 [≟] with or without a residual mass on 5PS [±]	Target nodes/nodal masses must regress to ≤ 1.5 cm in LDi
extralymphatic sites	It is recognized that in Waldeyer's ring or extranodal sites with high physiologic uptake or with activation within spleen or marrow (e.g., with chemotherapy or myeloid colony-stimulating factors), uptake may be greater than normal mediastinum and/or liver. In this circumstance, complete metabolic response may be inferred if uptake at sites of initial involvement is no greater than surrounding normal tissue even if the tissue has high physiologic uptake	No extralymphatic sites of disease
Non- measured lesion	Not applicable	Absent
Organ enlargement	Not applicable	Regress to normal
New lesions	None	None
Bone marrow	No evidence of FDG-avid disease in marrow	Normal by morphology; if indeterminate, IHC negative
Partial	Partial metabolic response	Partial remission (all of the following)
Lymph nodes and extralymphatic sites	Score 4 or 5 [±] with reduced uptake compared with baseline and residual mass(es) of any size	≥ 50% decrease in SPD of up to 6 target measurable nodes and extranodal sites
	At interim, these findings suggest responding disease	When a lesion is too small to measure on CT, assign 5 mm × 5 mm as the default value
	At end of treatment, these findings indicate residual disease	When no longer visible, 0×0 mm
		For a node > 5 mm × 5 mm, but smaller than normal, use actual measurement for calculation
Nonmeasured lesions	Not applicable	Absent/normal, regressed, but no increase
Organ enlargement	Not applicable	Spleen must have regressed by > 50% in length beyond normal

New lesions	None	None
Bone marrow	Residual uptake higher than uptake in normal marrow but reduced compared with baseline (diffuse uptake compatible with reactive changes from chemotherapy allowed). If there are persistent focal changes in the marrow in the context of a nodal response, consideration should be given to further evaluation with MRI or biopsy or an interval scan	Not applicable
No response or stable disease	No metabolic response	Stable disease

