Target nodes/nodal masses, extranodal lesions	Score 4 or 5 with no significant change in FDG uptake from baseline at interim or end of treatment	< 50% decrease from baseline in SPD of up to 6 dominant, measurable nodes and extranodal sites; no criteria for progressive disease are met
Non- measured lesions	Not applicable	No increase consistent with progression
Organ enlargement	Not applicable	No increase consistent with progression
New lesions	None	None
Bone marrow	No change from baseline	Not applicable
Progressive disease	Progressive metabolic disease	Progressive disease requires at least 1 of the following
Individual target nodes/nodal masses	Score 4 or 5 with an increase in intensity of uptake from baseline and/or	PPD progression:
Extranodal lesions	New FDG-avid foci consistent with lymphoma at interim or end-of-treatment assessment	An individual node/lesion must be abnormal with: LDi > 1.5 cm and Increase by ≥ 50% from PPD nadir and An increase in LDi or SDi from nadir 0.5 cm for lesions ≤ 2 cm 1.0 cm for lesions > 2 cm In the setting of splenomegaly, the splenic length must increase by > 50% of the extent of its prior increase beyond baseline (e.g., a 15-cm spleen must increase to > 16 cm). If no prior splenomegaly, must increase by at least 2 cm from baseline New or recurrent splenomegaly
Non- measured lesions	None	New or clear progression of pre- existing nonmeasured lesions
New lesions	New FDG-avid foci consistent with lymphoma rather than another etiology (e.g., infection, inflammation). If uncertain	Regrowth of previously resolved lesions A new node > 1.5 cm in any axis

	regarding etiology of new lesions, biopsy or interval scan may be considered	A new extranodal site > 1.0 cm in any axis; if < 1.0 cm in any axis, its presence must be unequivocal and must be attributable to lymphoma Assessable disease of any size unequivocally attributable to lymphoma
Bone marrow	New or recurrent FDG-avid foci	New or recurrent involvement

- Abbreviations: 5PS, 5-point scale; CT, computed tomography; FDG, fluorodeoxyglucose; IHC, immunohistochemistry; LDi, longest transverse diameter of a lesion; MRI, magnetic resonance imaging; PET, positron emission tomography; PPD, cross product of the LDi and perpendicular diameter; SDi, shortest axis perpendicular to the LDi; SPD, sum of the product of the perpendicular diameters for multiple lesions.

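### Inclusion 9 accepts a node of exactly 1.5 cm, which Appendix 1 does not call abnormal and which already meets its nodal size limit for complete response

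*Protocol*

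**What the plan says.** - **Entry.** Protocol 4.1, item 9, requires "CT measurable disease with at least 1 lesion having longaxis" of at least 1.5 cm, or splenomegaly. The synopsis has the same rule ("CT measurable disease with at least 1 lesion having long axis"). One lesion is enough, and the text says lesion, without separating nodal from extranodal disease.
- **Complete response on CT.** In Appendix 1, "Target nodes/nodal masses must regress to ≤ 1.5 cm in LDi". No percentage reduction is attached. The row is conjunctive: "Complete radiologic response (all of the following". The other conditions are no extralymphatic disease, non-measured lesions absent, organs back to normal, no new lesions and a normal marrow.
- **Partial and stable.** Partial remission needs a fall of at least 50% in SPD. Stable disease is "< 50% decrease from baseline in SPD of up to 6 dominant, measurable nodes and extranodal sites; no criteria for progressive disease are met".
- **Abnormal node.** For progression, "An individual node/lesion must be abnormal with: LDi > 1.5 cm", and among new lesions it lists "A new node > 1.5 cm in any axis".
- **Endpoint and rule.** Sections 2.2 and 12.1.1 define the primary outcome as best response (PR plus CR) on contrast-enhanced CT in the first 6 cycles. Section 12.6 takes the treatment forward on at least 9 responses in 30.

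**The concern.** The entry floor and the nodal CR ceiling are the same number, and both include it. A node of exactly 1.5 cm is measurable disease under inclusion 9, yet Appendix 1 does not call it abnormal and its size already satisfies the nodal CR limit. Just above that value, a change of a millimetre or two meets the CR size limit while falling well short of the 50% SPD reduction required for PR.

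Both CR and PR count as responses, so a patient with little or no real change could be scored as a responder. The go decision rests on 9 responses in 30, so a single misclassified patient shifts the error rate noticeably.

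**Working it through.** **1. The plan's own figures.** Inputs from Section 12.6: n = 30, cut-off 9, rates 20% and 40%. Exact binomial:
- P(X ≥ 9 | n = 30, p = 0.20) = 0.1287, stated as 13%.
- P(X ≥ 9 | n = 30, p = 0.40) = 0.9060, stated as 90%.

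Both reproduce, and the sample-size statement is not in dispute.

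**2. How far the overlap reaches.** Take a sole target node that shrinks proportionally in both diameters from LDi d to 1.5 cm. The fall in the product of diameters is 1 − (1.5/d)².

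| Baseline LDi (cm) | Fall in LDi | Fall in product |
|---|---|---|
| 1.5 | 0% | 0% |
| 1.6 | 6% | 12% |
| 1.7 | 12% | 22% |
| 1.8 | 17% | 31% |
| 2.0 | 25% | 44% |

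The fall reaches 50% at d = 1.5 × √2 = 2.12 cm. Below that, a node ending at 1.5 cm fits the stable-disease size row and also meets the nodal CR limit.

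**3. Reading error alone.** Assumptions, not given in the protocol: true size constant, readings rounded to the nearest mm, reading SD 1 mm. A 16 mm node reads 15 mm or less when the unrounded value is below 15.5 mm: P(Z < −0.5) = 0.31.
- One scan: 31%.
- Two scans: 1 − 0.69² = 52%.
- Three scans: 1 − 0.69³ = 67%.

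For a 17 mm node, P(Z < −1.5) = 7% on one scan and 19% on three. Varying the SD from 0.5 to 2 mm moves the three-scan figures to 40–79% (16 mm) and 0–54% (17 mm).

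Section 7.3.4 schedules CT after every 2 cycles, so three scans need 6 cycles without stopping. For scale, Section 1.1 cites a median PFS of 2.6 months in relapsed/refractory DLBCL in an earlier phase II mTOR-inhibitor study. That is about 11 weeks, between the first scan (8 weeks) and the second (16 weeks). Many non-responders would have one scan, so the lower figures are the more relevant ones.

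**4. Effect on the go decision at a true 20% rate.** If one patient is certain to be scored as a responder, 8 more are needed from 29:
- P(X ≥ 8 | n = 29, p = 0.20) = 0.2097, or 21.0%.

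If that patient responds truly with probability 0.20 and otherwise has a chance q of a false CR, the risk lies linearly between the two values: 0.1287 + q × (0.2097 − 0.1287).
- q = 0.3: 0.1287 + 0.3 × 0.0810 = 0.153.
- q = 0.6: 0.1287 + 0.6 × 0.0810 = 0.177.

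One such patient therefore moves the risk from 12.9% to about 15–18%. With none it stays at 12.9%.

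**The case against.** Four points can be made on the other side.

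- **The wording asks for regression.** Appendix 1 says nodes must regress to the limit, so a node unchanged at 1.5 cm has arguably not qualified. This stands in part: the unchanged case is open to argument. A change from 1.6 to 1.5 cm does satisfy the wording, and the mismatch between the entry rule and the definition of an abnormal node remains either way.
- **CR is conjunctive.** Any other node above 1.5 cm, extralymphatic or non-measured disease, an enlarged spleen or an involved marrow blocks it. This stands and sets the scope: patients entering on an extranodal lesion or on splenomegaly are not affected.
- **There are safeguards.** Section 7.3.4 asks for a trephine to confirm CR, and Section 12.2 provides for central review of scans. Neither removes the overlap. The trephine tests marrow, and central review may reduce reading noise but applies the same size limit.
- **The CR limit belongs to a published standard.** This stands. The limit itself is not at fault; the protocol's own entry threshold was set so that it meets it.

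A reader might infer that stable borderline nodes will commonly be scored as CR and that the false-go risk is really 20–31%. The documents do not support this. That range needs two or three affected patients with a 40–60% false-CR chance each. The protocol gives no distribution of baseline lesion sizes, and the upper false-CR chances assume several scans with no true change.

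**Conclusion.** The point holds in a limited form. Inclusion 9 accepts as measurable disease a node of exactly 1.5 cm that Appendix 1 does not treat as abnormal and that already meets the nodal size limit for CR. This is an internal inconsistency in the protocol and can be seen from the text alone.

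The effect on the primary endpoint is confined to patients whose whole disease is borderline nodal. Their number is not given and is probably small, possibly zero. The rise from 12.9% to about 15–18% for one such patient, or to 21.0% if the false CR is certain, is an illustration that depends on there being one. It is not an estimate of the trial's actual error rate.

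**What to change.** 1. **Eligibility (4.1 item 9 and synopsis).** Require a nodal lesion to have a long axis greater than 1.5 cm, matching Appendix 1. Leave the limit for extranodal lesions and the splenomegaly route unchanged. Because the current text says only lesion, the amendment must name nodal lesions; changing the symbol alone would tighten extranodal entry for no gain.
2. **Sensitivity analysis.** The first change removes only the exact 1.5 cm overlap; a 1.6 cm node stays eligible. For nodes slightly above the limit, keep the published criteria for the primary endpoint and add an analysis of the response rate that does not count a nodal CT CR with less than a 50% fall in SPD from baseline. Section 7.3.4 already requires the two-dimensional measurements.

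The 50% condition should not be written into the primary definition. That would depart from the adopted criteria and change the primary endpoint of an open-label single-arm trial after patients have been enrolled.

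Cost: a few patients with a sole 1.5 cm node become ineligible, and there is one extra analysis to report.

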4.2 Exclusion Criteria

Patients must not enter the study if any of the following exclusion criteria are fulfilled:

 Prior chemotherapy, biological therapy, radiation therapy, androgens, thalidomide, immunotherapy, other anticancer agents, and any investigational agents within 21days of registration (not including palliative radiotherapy at focal sites to non-target lesions). Corticosteroids are permitted during screening but should be weaned down to a maximum dose of prednisolone 10mg daily (or equivalent) by day 1 of cycle 1.

- With the exception of alopecia, any unresolved toxicities from prior chemotherapy should be no greater than CTCAE (Version 4.0) Grade 2 at the time of registration.

- 2. Major surgery within 4 weeks prior to entry to the study (excluding placement of vascular access), or minor surgery within 2 weeks of entry into the study.
- 3. Exposure to potent or moderate inhibitors or inducers of CYP3A4/5, Pgp (MDR1) and BCRP if taken within the stated washout periods before the first dose of study treatment. See Appendix 2.
- 4. Exposure to sensitive or narrow therapeutic range substrates of the drug transporters Pgp (MDR1), BCRP, MATE 1, MATE 2K, OATP1B1 and OATP1B3, within the appropriate wash-out period (a minimum of 5 x the reported terminal elimination half-life of each drug) before the first dose of study treatment. See table in appendix 3.
- 5. Previous treatment with any first generation mTORC1 inhibitors (rapamycin, sirolimus, temsirolimus, everolimus) or any dual mTORC1/2 inhibitors (e.g. AZD2014, AZD8055).
- 6. Patients who have experienced intolerable AEs prejudged by the treating Investigator due to other mTORC1 or mTORC1/2 inhibitors, PI3 kinase inhibitors, or AKT inhibitors.
- 7. Patients with proven central nervous system (CNS) involvement.
- 8. As judged by the Investigator, any evidence of severe or uncontrolled systemic diseases (e.g., severe hepatic impairment, interstitial lung disease (e.g.bilateral, diffuse, parenchymal lung disease), uncontrolled chronic renal diseases (e.g. glomerulonephritis, nephritic syndrome, Fanconi Syndrome or Renal tubular acidosis) or current unstable or uncompensated respiratory or cardiac conditions, or uncontrolled hypertension, active bleeding diatheses or active infection. Screening for chronic conditions is not required.
- 9. Patients who have experienced any of the following procedures or conditions currently or in the preceding 12 months:

- coronary artery bypass graft
- angioplasty
- vascular stent
- myocardial infarction
- angina pectoris
- congestive heart failure New York Heart Association Grade ≥2
- ventricular arrhythmias requiring continuous therapy
- supraventricular arrhythmias including atrial fibrillation, which are uncontrolled
- haemorrhagic or thrombotic stroke, including transient ischaemic attacks or any other central nervous system bleeding
- 10. Abnormal echocardiogram (ECHO) or multi-gated acquisition scan (MUGA) at screening (left ventricular ejection fraction [LVEF] <50%).
- 11. Torsade's de Pointes within 12 months of study entry.
- 12. Patients with uncontrolled diabetes Type I or uncontrolled Type II (HbA1c >7 mmol/L assessed locally) as judged by the local investigator.
- 13. Inadequate bone marrow reserve or organ function as demonstrated by any of the following laboratory values unless due to underlying NHL infiltration.
 - Absolute neutrophil count <1.5 x 10⁹/L (without GCSF / GMCSF support)
 - Platelet count <100 x 10⁹/L
 - Haemoglobin <90 g/L (transfusions permissible)

- Alanine aminotransferase (ALT) or aspartate aminotransferase (AST) >2.5 times the upper limit of normal (ULN) if no demonstrable liver involvement or >5 times ULN in the presence of liver involvement

- Total bilirubin >1.5 times ULN unless in the presence of Gilbert's syndrome with an elevated indirect fraction

- Serum creatinine >1.5 times ULN concurrent with creatinine clearance ≤50 mL/min (measured or calculated by Cockcroft and Gault equation); confirmation of creatinine clearance is only required when creatinine is >1.5 times the ULN

- 14. Current refractory nausea and vomiting, chronic gastrointestinal diseases, inability to swallow the formulated product or previous significant bowel resection or gastrointestinal disease that would preclude adequate absorption of AZD2014.
- 15. History of known hypersensitivity to active or inactive excipients of AZD2014 or drugs with a similar chemical structure or class to AZD2014.
- 16. Judgment by the Investigator that the patient is unsuitable to participate in the study and the patient is unlikely to comply with study procedures, restrictions and requirements.
- 17. Previous history of other active malignant disease other than fully excised basal or squamous cell carcinoma of the skin, carcinoma in situ of the uterine cervix or localised disease treated with curative intent using surgery alone, within the last 3 years.

For the rituximab cohort only, patients must not enter the study if any of the above or below exclusion criteria are fulfilled:

- 18. Known hypersensitivity to recombinant proteins, murine proteins or to any excipients of rituximab infusions
- 19. Vaccination with live virus vaccine within the 4 weeks prior to study entry or intention to do so during the study treatment

5. SCREENING AND CONSENT

5.1 Screening

For patients who appear to meet the criteria for participation in the study, the Investigator will provide information to allow them to make an informed decision regarding their participation. Investigators will be expected to maintain a Screening Log of all potential study candidates. This Log will include limited information about the potential candidate (e.g. year of birth and gender), the date and outcome of the screening process (e.g. enrolled into study, reason for ineligibility, or declined participation).

If informed consent is given (see section 5.2), the Investigator will conduct a full screening evaluation to ensure that the patient satisfies all inclusion and exclusion criteria. A patient who gives written informed consent and who satisfies all the inclusion and exclusion criteria may be registered onto the study. Note that assessments conducted as standard of care do not require informed consent and may be provided as screening data if conducted within the stipulated number of weeks prior to registration. Assessments required in screening are listed in the assessments table and detailed in section 5.1.1.

